## **8. EFFICACY ANALYSES**

### **8.1. Adjustments for Covariates**

For comparison of treatment groups with respect to change and percent change from baseline, analysis of covariance (ANCOVA) and restricted maximum likelihood (REML) based mixed model repeated measures (MMRM) models will be used. The corresponding baseline value will be used as a covariate in the model.

### **8.2. Handling of Dropouts or Missing Data**

Primary analyses will be based on observed data. Sensitivity analyses will be conducted for patients who do not have data at the Week 12 visit, where the last on treatment value will be used for Week 12.

### **8.3. Interim Analyses and Data Monitoring**

No data monitoring committees are planned for this study.

An interim analysis will be performed after all patients in Part 1 have completed Week 6 assessments. Blinded adverse event and laboratory data will be reviewed. PK and PD data will be provided to the Sponsor with a dummy subject identification and treatment assignment. If robust VAP-1/SSAO activity suppression is observed, and available PK suggest a lower dose may also possibly lead to robust VAP-1/SSAO activity suppression, enrollment in Part 2 with 4 mg TERN-201 may be initiated. Additionally, if safety data indicates 10 mg TERN-201 is overall safe and well-tolerated and anticipated exposures with a higher dose remain below the exposure limit (see section 4.3 of the protocol), enrollment in Part 2 to assess a dose up to 20 mg TERN-201 in Part 2 may be initiated.

Additionally, an interim analysis will be conducted after the completion of Part 1. All data from Part 1 will be cleaned and locked prior to unblinding and analyses.

### **8.4. Multicenter Studies**

The randomization is not stratified by site. Likewise, analyses of data will not be stratified by study site.

## **8.5. Use of an “Efficacy Subset” of Patients**

Not Applicable.

## **8.6. Multiple Comparisons/Multiplicity**

There will be no adjustment for multiplicity. Statistical testing will be considered nominal, descriptive and exploratory.

## **8.7. Pharmacokinetic (PK) Analyses**

Analyses of trough PK concentrations will use the PK Analysis Set. Analyses of intensive PK concentrations and PK parameters will use the PK/PD Substudy Analysis Set. All PK endpoints, recorded and derived, will be presented in by-patient data listings.

Plasma and urine TERN-201 and metabolite (TRN-001021 and TRN-001744) concentrations will be used as supplied by the analytical laboratory for PK analysis. The units of concentration and resulting PK parameters, with amount or concentration in the unit, will be presented as they are received from the analytical laboratory, with the exception of metabolite to parent ratios which will be corrected for differences in molecular weight. Urine volume will be presented with urine concentrations. Urine collection dates and times from the EDC will be used for analyses, otherwise plasma collection dates and times from the central vendor will be used.

Blood and urine samples will be collected at the timepoints specified in Appendix 2 of the study protocol.

### **8.7.1. Below the Quantification Level (BLQ) Values**

Plasma concentration values that are BLQ will be set to zero, with defined exceptions as follows:

- Any embedded BLQ value (between 2 quantifiable concentrations) and BLQ values following the last quantifiable concentration in a profile will be set to missing for the purposes of PK analysis. If an embedded BLQ value is considered anomalous within the concentration time profile, this value will be excluded as well.
- If there are late positive concentration values following 2 BLQ concentration values in the apparent terminal phase, these values will be evaluated. If these values are considered to be anomalous (see [Section 8.9.2](#)), they will be set to missing.

If an entire plasma concentration-time profile is BLQ, the profile will be excluded from the PK analysis.

Urine concentrations below lower limit of quantification (LLOQ) will be treated as numerical zero for the calculation of the urine parameters.

### **8.7.2. Anomalous Values**

If a value is considered to be anomalous due to being inconsistent with the expected PK profile, it may be appropriate to exclude this point from the PK analysis. However, the exclusion of data must have strong justification and will be documented in the raw data and CSR.

### 8.7.3. Concentration-Time Data

Individual plasma TERN-201 and metabolite (TRN-001021 and TRN-001744) concentration data will be listed separately for trough concentrations (PK Analysis Set) and trough and intensive concentrations (PK/PD Substudy Analysis Set). Concentrations will be summarized by nominal sampling time point and treatment with descriptive statistics (number of non-missing observations, arithmetic mean, arithmetic SD, arithmetic coefficient of variation [CV%], median, Q1, Q3, minimum, maximum, geometric mean and geometric CV%). The number of values below quantification limit (BLQ) will be presented for all patients and separately for PK/PD substudy patients. Individual urine TERN-201 and metabolite (TRN-001021 and TRN-001744) concentrations and sample volume will be listed for each patient.

The following rules will be applied in the presentation of plasma concentration data if there are values that are BLQ or if there are missing values (e.g., no result [NR]) in a plasma concentration data series to be summarized.

- For the calculation of summary statistics, BLQ values will be set to zero.
- For the calculation of PK parameters, BLQ values will be set to zero prior to the first measurable concentration and set to missing after a measurable concentration is observed.
- If an embedded BLQ value is considered anomalous within the concentration time profile, this value will be excluded from the summary statistics.
- Where there is NR, these will be set to missing.
- If there are less than three values in the data series, only the minimum, maximum and number of observations will be presented. The other summary statistics will be denoted as not calculated (NC). BLQ is considered a value.
- If all the values are BLQ, then the arithmetic mean, arithmetic SD, median, minimum and maximum will be presented as zero, and the geometric mean and geometric CV% will be denoted as NC.
- If the value of the arithmetic mean or median is below the lower limit of quantification, these values will be presented as zero and the geometric mean and geometric CV% will be denoted as NC.

Individual patient and arithmetic mean concentration-time profiles, for TERN-201 and its metabolites (TRN-001021 and TRN-001744), for each TERN-201 dose, will be presented graphically on linear and logarithmic concentration scales separately for trough concentrations (PK Analysis Set) and trough and intensive concentrations (PK/PD Substudy Analysis Set) for Week 0/Day 1 and Week 12. A reference line for LLOQ will be included on graphs.

Concentration data in listings will be presented to the same number of significant figures as provided by the analytical laboratory. Descriptive statistics will be displayed according to the rules outlined in [Section 3.2](#).

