Plasma exposures to TERN-201 were greater than dose proportional. TERN-201 was rapidly cleared from plasma. Steady state was achieved in the highest dose group (10 mg) after Day 7 of dosing. The half-life of TERN-201 increased with dose, suggesting saturable, target-mediated clearance.

Single and multiple doses of TERN-201 significantly suppressed plasma total amine oxidase activity at all doses studied. Using an exploratory assay to assess the effect of TERN-201 on VAP-1/SSAO-specific amine oxidase activity in the plasma, near complete inhibition (>80% with 1 mg, > 90% with 10 mg) was observed after only a single dose on Day 1 (achieved within 4 hours after dosing) with sustained suppression over the dosing period in MAD cohorts. Dose-dependent increases in methylamine, an endogenous substrate of VAP-1/SSAO predicted to increase upon VAP-1/SSAO inhibition, were observed after the first dose of TERN-201 and continued to increase in a dose-dependent manner after multiple doses of TERN-201.

Based on the exploratory assessment on plasma PK of two TERN-201 metabolites, TRN-001021 and TRN-001744, the percentages of either metabolite AUC relative to the total TERN-201-related plasma AUC (sum of TERN-201, TRN-001021, and TRN-001744) were calculated. Median TRN-001021 AUC was <10% and 13.7% of the total plasma AUC associated with TERN-201 in the 4 mg and 10 mg groups, respectively. Median TRN-001744 AUC was 11.5% and <10% of the total plasma AUC associated with TERN-201 in the 4 mg and 10 mg groups, respectively.

Additional details on Study TERN201-US-A101 are available in the Investigator's Brochure.

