### 8.7.4. Plasma Pharmacokinetic Parameters

Sparse PK samples may be used to calculate PK parameters using population pharmacokinetic (Pop PK) modeling. Data from the study may be combined with data from other studies for the

purposes of Pop PK modeling. If Pop PK modeling is performed, the process will be described in a separate analysis plan.

For the purposes of this SAP, plasma PK parameters will be computed for the PK/PD sub-study patients only. Plasma PK parameters for TERN-201 and its metabolites (TRN-001021 and TRN-001744) will be calculated from the individual plasma concentrations using a non-compartmental approach for Week 0/Day 1, Week 6, and Week 12. Week 0/Day 1 and Week 6 will include pre dose and all post dose assessments prior to the next dose. Week 12 will include pre dose and all post dose assessments. The actual PK sampling times will be used for the PK analysis. If actual PK sampling times are missing, nominal times will be used. If the 24 hr sample is missing at Week 6 or Week 12, the predose sample concentration may be re-used for the 24 hr sample for the purposes of calculating PK parameters, if appropriate.

**Table 6** presents the plasma PK parameters for TERN-201 and its metabolites (TRN-001021 and TRN-001744) to be calculated.

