T min	Time of the minimum observed plasma concentration, obtained directly from the plasma concentration-time profiles at steady state, within the sampling interval, i.e. calculated for each intensive sampling visit separately (Week 6 Week 12). In the case where multiple minimum are of equal magnitude, the time of the latest minimum will be reported as T min .
T last	Time of the last quantifiable plasma concentration, obtained directly from the plasma concentration-time profiles within the sampling interval, i.e. calculated for each intensive sampling visit separately (Week 0/Day 1, Week 6, Week 12).
t 1/2	Apparent plasma terminal elimination half-life, calculated as $\ln(2) / \lambda_z$ .
CL/F	Apparent total plasma clearance calculated as Dose / AUC 0-∞ for Week 0/Day 1
CL ss /F	Apparent total plasma clearance at steady state, calculated as Dose / AUC τau for Week 6 and Week 12.
V z /F	Apparent volume of distribution, calculated as Dose / ( $\lambda_z * AUC_{0-∞}$ ) for Week 0/Day 1
V ss /F	Apparent volume of distribution, calculated as Dose / ( $\lambda_z * AUC_{τau}$ ) for Week 6 and Week 12.
RA AUCτau	Observed accumulation ratio based on AUC τau calculated as AUC τau (Week 6 and Week 12) / AUC 0-24hr (Day 1).
RA Cmax	Observed accumulation ratio based on C max , calculated as C max (Week 6 and Week 12) / C max (Day 1).
LR	Linearity ratio calculated as AUC τau (Week 6 and Week 12) / AUC 0-∞ (Day 1)
C avg	Average observed drug concentration at steady state (Week 6 and Week 12 only)
C 24	For Week 0/Day 1, observed drug concentration at the end of the dosing interval, e.g. from 0 to 24 hours
C τau	Observed drug concentration at the end of the dosing interval, e.g. from 0 to 24 hours (Week 6 and Week 12 only)
λ z	Apparent terminal rate constant (listed only)

In addition, the metabolite-to-parent ratios will be calculated for AUCτau, Cτau, and Cmax. Metabolite-to-parent ratios will be corrected for molecular weight differences by multiplying the ratio by a correction factor. The correction factor for TRN-001021 ratios is 1.05 and the correction factor for TRN-001744 ratios is 1.42.

Additional PK parameters may be determined where appropriate.

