### 8.9. Exposure Response Analyses

The plasma PK parameters  $AUC_{tau}$ ,  $C_{max}$ , and  $C_{tau}$  will be used to evaluate exposure-response. PK parameters will be set to 0 for the placebo group for the purpose of PK/PD.

Pharmacodynamic exposure-response analyses of plasma VAP-1/SSAO activity and methylamine concentration PD parameters will be performed using several exposure-response models for the PK/PD Analysis Set, including but not limited to linear, quadratic, exponential, and  $E_{max}$ . The best fit significant model will be chosen based on AIC, the smaller the AIC value the better the model fit.

Additional exposure-response and dose-response (as applicable) analyses may be explored for baseline patient characteristics such as sVAP-1, BMI, diabetes mellitus, or other characteristics or additional efficacy, safety, and PD endpoints, as needed. These analyses will be described in a separate document.

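### A 24-hour sample below quantification (BLQ) is set to missing for C24 and Ctau: the summaries run high, and entry into the Ctau exposure-response analysis is undefined

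*SAP*

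**What the plan says.** - **BLQ rule for parameters.** SAP 8.7.3 counts a BLQ value as zero before the first measurable concentration; later ones are "set to missing after a measurable concentration is observed". SAP 8.7.1 agrees for the end of a profile: "BLQ values following the last quantifiable concentration in a profile will be set to missing for the purposes of PK analysis". A profile that is BLQ throughout is excluded.
- **The parameters affected.** SAP Table 6 defines C24 (Day 1) and Ctau (Weeks 6 and 12) as the observed concentration at the end of the 24-hour interval. SAP 8.7.5 leaves missing values out of parameter summaries.
- **Exposure-response.** SAP 8.9 uses AUCtau, Cmax and Ctau. It adds: "PK parameters will be set to 0 for the placebo group for the purpose of PK/PD". Linear, quadratic, exponential and Emax models are among the candidates, chosen by AIC. The section has no BLQ rule.
- **A possible fallback.** If the 24-hour sample is missing at Week 6 or 12, SAP 8.7.4 says "the predose sample concentration may be re-used for the 24 hr sample for the purposes of calculating PK parameters, if appropriate". Day 1 is not covered.
- **Other BLQ conventions.** SAP 8.7.3 sets BLQ to zero in concentration summaries and counts BLQ values. SAP 8.8.1 uses half the limit for PD values.
- **Background.** Protocol 2.2.2 reports that "TERN-201 was rapidly cleared from plasma", with more than 80% inhibition at 1 mg and more than 90% at 10 mg after one dose, sustained over repeated dosing.

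**The concern.** Setting trailing BLQ values to missing is reasonable for AUC and the terminal slope, which use the whole profile. For C24 and Ctau the trailing sample is the parameter. Setting it to missing removes a patient because the value is low, and the remaining values overstate the typical trough. TERN-201 PK parameters are a secondary endpoint, so this affects more than the exploratory modelling.

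In SAP 8.9 the two ends of the exposure scale are treated differently: placebo enters at 0, while a treated patient with a trough just below the LLOQ has no value. With an irreversible inhibitor, such a patient may still be well suppressed, and so is informative about whether trough concentration drives the effect. The SAP does not say whether that patient is dropped, kept with a measured predose value, or kept at 0. These choices can give different fitted models.

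**Working it through.** **No figure to reproduce.** The documents give no LLOQ, BLQ rate, trough variability or exposure-response estimate. All sizes below rest on stated assumptions.

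**Patients at risk.** From SAP 2.2, treated sub-study patients number about 8 in Part 1 and 6 + 6 in Part 2, so 8 + 6 + 6 = 20 at most, and 8 if Part 2 does not enrol. Placebo is 4 + 3 = 7. At 25% BLQ, 20 treated become 15.

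**Bias in the C24 and Ctau mean.** Take troughs as lognormal with coefficient of variation CV, and let a share p fall below the LLOQ.

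- s = sqrt(ln(1 + CV²)). With CV 60%, s = sqrt(ln 1.36) = 0.5545.
- z = the standard normal quantile at p. With p = 0.25, z = -0.6745.
- Mean after dropping ÷ true mean = Φ(s - z)/(1 - p) = Φ(1.229)/0.75 = 0.8905/0.75 = 1.19.
- With half the LLOQ: LLOQ/median = exp(zs) = 0.688 and mean/median = exp(s²/2) = 1.166. The ratio is 0.8905 + 0.25 × 0.344/1.166 = 0.96.

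| BLQ share (CV 60%) | Dropped | Half LLOQ |
|---|---|---|
| 10% | 0.9668/0.90 = 1.07 | 0.99 |
| 25% | 0.8905/0.75 = 1.19 | 0.96 |
| 50% | 0.7104/0.50 = 1.42 | 0.93 |

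This bias does not depend on any exposure-response model.

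**Exposure-response with BLQ patients dropped.** Simulated sub-studies had 6/8/6 patients on 4/10/20 mg, 7 placebo at 0, lognormal Ctau (CV 50%) rising as dose^1.3, and response SD 5 points. There were 1,500 runs per setting for linear fits and 200 for Emax fits. Entries show the fit with true Ctau, then with BLQ patients dropped.

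| True response; fitted model | 10% BLQ | 30% BLQ | 50% BLQ |
|---|---|---|---|
| Linear; linear slope | -20.0, -20.0 | -20.0, -20.0 | -20.0, -20.0 |
| Emax (EC50 half the median 10 mg trough); Emax | -95.5, -95.2 | -95.3, -95.6 | -95.5, -94.7 |
| Saturated; Emax | -95.4, -95.3 | -94.9, -94.9 | -95.1, -96.0 |
| Saturated; linear slope | -19.7, -21.5 (+9%) | -19.7, -25.5 (+29%) | -19.2, -27.4 (+43%) |

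Dropping matters to the fitted relation when a straight line is put through a saturated response, and hardly at all when the shape is right.

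**Exposure-response with predose re-use.** A BLQ predose value precedes the first measurable concentration of its profile, so SAP 8.7.3 makes it 0. If that 0 is carried into Ctau, a suppressed treated patient has placebo exposure. The extreme case, with every BLQ patient at 0 and a saturated response, gave these Emax fits at 10/30/50% BLQ:

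- E0 of -18, -41 and -53, where about 0 is right.
- Emax of -78, -55 and -43, where about -95 is right.

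In separate simulations of the same sub-study size, AIC chose the linear model in 12 of 150 fits at 25% BLQ and 127 of 150 at 50% BLQ when BLQ was 0. It chose it in none of 150 when BLQ patients were dropped or given half the LLOQ.

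**Exposure-response with half the LLOQ.** For the saturated response the linear slope was -19.6, -19.3 and -19.5 at 10/30/50% BLQ, against -19.7, -19.7 and -19.2 with true Ctau. At 30% BLQ the fitted Emax was -95.1, against -94.9.

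**The case against.** A reader might infer that the plan as written overstates the exposure-response relation. The documents do not support that. Assume a flat 92% suppression (SD 4) in all treated patients, placebo SD 12 and Ctau CV 60%. A straight-line fit then has R-squared 0.62 with BLQ patients dropped against 0.41 at half the LLOQ (25% BLQ), and 0.76 against 0.38 (50% BLQ). But SAP 8.9 selects by AIC from a list that includes Emax. In 300 runs of that setting, taking the exponential model in its saturating form, AIC never chose the straight line under either handling. It chose a saturating model in at least 97% of runs. The Emax fit barely moved: at 25% BLQ, R-squared was 0.974 both ways and Emax was -93.3 against -92.6. This part of the objection stands.

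It also stands that the BLQ rate is unknown. Protocol 2.2.2 reports a half-life that rises with dose, so BLQ troughs at the higher doses are not obvious. With 6/8/6 patients, a 50% rate would need all of the 4 mg group plus four patients on a higher dose. Cmax is untouched, and AUCtau remains calculable if the three-concentration rule in SAP 8.7.4.2 is met. Testing is nominal and exploratory under SAP 8.6. BLQ counts in the concentration tables would keep low troughs visible.

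Predose re-use does not answer the point. It is discretionary, does not cover Day 1, and does not say whether a BLQ value set to missing counts as a missing sample. Where it brings in a 0, it does more harm to the fit than dropping the patient.

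**Conclusion.** The point holds in a limited form. The C24 and Ctau summaries are biased upward whenever treated 24-hour samples are BLQ: by about 19% at an assumed 25% BLQ and CV 60%, with a range of 7% to 42% for 10% to 50% BLQ.

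For the Ctau analysis in SAP 8.9, the handling of these patients is not fixed. By default they are lost from an already small group. Predose re-use may instead place them at placebo exposure, which can distort the Emax fit and change the model AIC selects.

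A general claim of overstatement is not supported. Dropping can inflate a linear slope fitted to a saturated response, by 9% to 43% in the runs above, but a correctly shaped Emax fit hardly changes. All sizes depend on a BLQ rate, a trough variability and a response shape that the documents do not give. The point is worth correcting because the summary bias needs no model and a short stated rule removes the ambiguity.

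**What to change.** In SAP 8.7.1, 8.7.3 and 8.9:

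1. Exempt C24 and Ctau from the set-to-missing rule. For treated patients, use half the LLOQ for a BLQ 24-hour value in parameter summaries and exposure-response, in line with SAP 8.8.1 for PD values. Keep set-to-missing for the terminal slope and AUC.
2. State that predose re-use in 8.7.4 does not apply to a sample that was taken and found BLQ.
3. Do not compute Ctau metabolite-to-parent ratios from imputed values, since they would reflect assay limits.
4. Report the number of BLQ 24-hour samples by dose and visit.
5. Repeat the Ctau exposure-response analysis with BLQ patients excluded, as a sensitivity analysis.

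The cost is a few sentences and one extra model run, with no new data, and should be settled before unblinding. The drawback is that any value below the LLOQ is arbitrary. At CV 60%, half the LLOQ puts the mean about 1% low at 10% BLQ and 7% low at 50%. Item 5 shows whether the choice matters. Setting treated BLQ values to 0 to match placebo is not a good substitute, given the distorted Emax fits above.

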### 8.7.4. Plasma Pharmacokinetic Parameters

Sparse PK samples may be used to calculate PK parameters using population pharmacokinetic (Pop PK) modeling. Data from the study may be combined with data from other studies for the

purposes of Pop PK modeling. If Pop PK modeling is performed, the process will be described in a separate analysis plan.

For the purposes of this SAP, plasma PK parameters will be computed for the PK/PD sub-study patients only. Plasma PK parameters for TERN-201 and its metabolites (TRN-001021 and TRN-001744) will be calculated from the individual plasma concentrations using a non-compartmental approach for Week 0/Day 1, Week 6, and Week 12. Week 0/Day 1 and Week 6 will include pre dose and all post dose assessments prior to the next dose. Week 12 will include pre dose and all post dose assessments. The actual PK sampling times will be used for the PK analysis. If actual PK sampling times are missing, nominal times will be used. If the 24 hr sample is missing at Week 6 or Week 12, the predose sample concentration may be re-used for the 24 hr sample for the purposes of calculating PK parameters, if appropriate.

**Table 6** presents the plasma PK parameters for TERN-201 and its metabolites (TRN-001021 and TRN-001744) to be calculated.

